Important protocol deviations will be defined prior to first participants enrolled. Participants will not be excluded from analysis sets on the basis of any important protocol deviations. The definitions of each category of important protocol deviation will be fully specified in the SAP. Details regarding statistical analysis will be provided in the SAP. In general, continuous endpoints will be summarised using the mean, the standard deviation, median, minimum value, and maximum value, and the categorical endpoints will be summarised using frequency counts and percentages. Two-sided 95% CI for proportions computed using exact Clopper-Pearson method may also be presented. Time to event data will be presented graphically using Kaplan Meyer curve.

In general, all data up to Week 28 or Week 52 will be included in the analysis, even if a participant discontinues treatment or changes background therapy other than OCS (treatment policy strategy). If a participant initiates therapy with other biologic for treatment of asthma, then only data collected up until the initiation of the other biologic treatment will be included in the analysis (hypothetical strategy).

In general, efficacy analyses will be based on planned treatment period, starting on the date of first dose of IP and ending on the date of the Week 28 or Week 52 visit or earlier study withdrawal date.

Safety analyses will be based on-treatment and/or on-study period. Details will be specified in the SAP. On-treatment period starts on the date of first dose of IP and ends on minimum (date of last dose of IP + 33 days, date of death, date of study withdrawal). On-study period (planned treatment and follow-up) starts on the date of first dose of IP and ends on the study completion or withdrawal date. Data will be listed in participant-level data listings.

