Rate of asthma exacerbation associated with hospitalisation or emergency room (ER) visit over 28 weeks and over 52 weeks		(other than OCS): all data included in the analysis - Initiation of therapy with another biologic for treatment of asthma: only data collected up until the initiation of the other	95% CI	4.2.3
Rate of asthma exacerbation associated with hospitalisation over 28 weeks and over 52 weeks		biologic treatment is included in the analysis.		
Proportion of participants who did not experience an exacerbation over 28 weeks and over 52 weeks			Proportion of participants with	4.2.4
Proportion of participants who did not experience an exacerbation associated with hospitalisation or ER visit over 28 weeks and 52 weeks			95% CI	
Proportion of participants who did not experience an exacerbation associated with hospitalisation over 28				

weeks and over 52 weeks

Endpoint	Popula tion	Intercurrent event strategy	Population level summary (analysis)	Details in section
Secondary objective: To assess the ability of tezepelur	mab 210 m	Secondary objective: To assess the ability of tezepelumab 210 mg SC to allow reduction of the prescribed OCS dose without loss of asthma control ^a	of asthma controla	
Proportion of participants with \geq 50% reduction from baseline in daily maintenance OCS dose at Week 28 and Week 52	FAS	Same intercurrent event strategies as for primary objective.	Proportion of participants with 95% CI	4.2.5
Categorised percent reduction from baseline in the daily maintenance OCS dose at Week 28 and Week 52				4.2.6
Absolute and percent change from baseline in daily maintenance OCS dose at Week 28 and Week 52		Same intercurrent event strategies as described for secondary objective related to exacerbation.	Least Square (LS) mean with 95% CI	4.2.7
Secondary objective: To assess the ability of tezepelumab to improve lung function	mab to imp	rove lung function		
Change from baseline in post-BD FEV ₁ at Week 28 and Week 52	FAS	Same intercurrent event strategies as described for secondary objective related to exacerbation.	LS mean with 95% CI	4.2.8
Secondary objective: To assess the ability of tezepelumab to improve asthma control ^a	mab to imp	rove asthma control ^a		
Change from baseline in Asthma Control Questionnaire 6 (ACQ-6) at Week 28 and Week 52	FAS	Same intercurrent event strategies as described for secondary objective related to exacerbation.	LS mean with 95% CI	4.2.9

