4.2.4.1 Definition

There are three proportions to assess this secondary endpoint:

- Proportion of participants who did not experience an exacerbation,
- Proportion of participants who did not experience an exacerbation associated with hospitalization or ER visit,
- Proportion of participants who did not experience an exacerbation associated with hospitalization.
- Each of those proportion of participants (i.e., who did not experience an exacerbation; an exacerbation associated with hospitalization or ER visit; an exacerbation associated with hospitalization only) are calculated over 28 weeks and over the 52-week period.

4.2.4.2 **Derivations**

For considering a participant without any experience of exacerbation, the planned treatment period defined in Section 3.3.1.1 has to be considered. A participant is considered to have completed the planned treatment period, if the planned treatment period is greater than

- than 191 (Day 196 minus 5) for the analysis at Week 28
- 359 days (Day 364 minus 5, to account for visit windowing) for the analysis at Week 52

Participants who had no asthma exacerbations during the planned treatment period and who completed the period of interest (up to Week 28 or Week 52) without initiating another biologic are defined as exacerbation free/successful outcome [a].

Participants who did not complete the planned treatment period or initiate another biologic during the planned treatment period are defined as not having a successful outcome for this endpoint [b] [c].

Participants who completed the planned treatment period without initiating another biologic and had an asthma exacerbation are defined as not having a successful outcome for this endpoint [d].

	No asthma exacerbation	Asthma exacerbation
Completed planned treatment period without initiating another biologic	[a] Exacerbation free/successful outcome	[d] No successful outcome
Did not complete treatment period or initiate another biologic during the planned treatment period	[b] No successful outcome	[c] No successful outcome

The proportion is calculated as the number of participants with a successful outcome at Week 28/Week 52 divided by total number of participants in the FAS population.

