The proportion of participants free from exacerbations that required hospitalisation or ER visits (or hospitalization only) during the planned treatment period is calculated similarly. A participant who only had an exacerbation which did not lead to hospitalisation or ER visit (or hospitalisation only) is considered a successful outcome for this endpoint.

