4.2.4.3 Handling of Dropouts and Missing Data

No data imputation.

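### The exacerbation-free proportions count event-free starters of another biologic, and event-free study withdrawals, as failures; for biologic starters this contradicts the strategy the SAP states

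*SAP*

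**What the plan says.** SAP 4.2.4 covers three secondary proportions: no exacerbation, none with hospitalisation or an ER visit, and none with hospitalisation. Each is taken over 28 and over 52 weeks. Under 4.2.4.2, participants who do not complete the planned treatment period "or initiate another biologic during the planned treatment period are defined as not having a successful outcome". The two-by-two table in that section has a cell marked [b] for people with no exacerbation who did not complete or who started another biologic; it is scored as unsuccessful. Completion means more than 191 days at Week 28 and more than "359 days (Day 364 minus 5, to account for visit windowing) for the analysis at Week 52". The number of successes is "divided by total number of participants in the FAS population". For the severe-event versions, the proportion free of hospitalisation or ER visits ("or hospitalization only) during the planned treatment period is calculated similarly". SAP 4.2.4.3 adds "No data imputation".

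The strategy for these endpoints is set elsewhere. The SAP 4.2 table, for the whole exacerbation objective, has the entry "Initiation of therapy with another biologic for treatment of asthma: only data collected up until the initiation of the other" biologic is analysed. Protocol 9.4.1 has the same general rule: "only data collected up until the initiation of the other biologic treatment will be included in the analysis (hypothetical strategy". SAP Section 2 states that nothing differs from the current protocol.

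**The concern.** Someone who starts another biologic without having had an exacerbation should, under the stated strategy, contribute event-free follow-up to that date and nothing after it. SAP 4.2.4.2 scores that person as a failure. The rate endpoint under the same objective does follow the stated strategy: SAP Table 5 ends time at risk when another biologic starts. So two endpoints with one declared strategy treat the same person differently.

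Event-free study withdrawals are also scored as failures. The resulting figure is labelled as the proportion with no exacerbation, yet it measures completing the period with no exacerbation and no other biologic. In a single-arm study whose purpose is estimation, no comparator arm absorbs the difference. The rule also carries into every subgroup analysis (SAP 4.2.4.6).

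**Working it through.** **Passages side by side**

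| Situation, no exacerbation observed | Stated strategy | SAP 4.2.4.2 |
|---|---|---|
| Starts another asthma biologic | Data up to initiation only (SAP 4.2 table, Protocol 9.4.1) | Failure |
| Withdraws from the study | Not listed in the table; full analysis set includes data up to termination (SAP 3.2.2) | Failure |
| Stops tezepelumab, stays in the study | All data used (SAP 4.2 table) | Judged on observed data, because the planned treatment period runs to Week 52 or study withdrawal (SAP 3.3.1.1) |

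The first row is a contradiction, the second is an undeclared choice, and the third is consistent.

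**The plan's own figure.** Protocol 9.2 and SAP 1.3 give a Clopper-Pearson 95% half-width of 5.8 points at 50% with N = 300. Recomputed from beta quantiles it is 5.80. This is the scale against which to judge any shift.

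**Inputs.** N = 300 and the Clopper-Pearson method come from the documents. They give no exacerbation-free proportion, hospitalisation risk or leaving rate, so these are assumed: p is the true 52-week event-free proportion, and w is the share who withdraw or start another biologic. Leaving is taken as unrelated to the event.

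**Formulas**
- Reported value: p(1 − w). A success must be event-free and must not have left.
- Share of failures that are leavers with no observed event: w·q / [1 − p(1 − w)], where q is the chance that a leaver has no event before leaving. With a constant hazard λ = −ln p and leaving times uniform over 52 weeks, q = (1 − p)/λ. This gives q = 0.40/0.511 = 0.783 for p = 60%, and q = 0.05/0.0513 = 0.975 for p = 95%.

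**Results** (intervals use counts rounded to whole participants)

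| True p | w | Reported | 95% CI, N = 300 | Failures that are event-free leavers |
|---|---|---|---|---|
| 60%, any exacerbation | 2% | 58.8% | 52.9 to 64.3 | 4% |
| 60% | 5% | 57.0% | 51.2 to 62.7 | 9% |
| 60% | 10% | 54.0% | 48.2 to 59.7 | 17% |
| 95%, hospitalisation | 2% | 93.1% | 89.5 to 95.6 | 28% |
| 95% | 5% | 90.25% | 86.4 to 93.4 | 50% |
| 95% | 10% | 85.5% | 80.8 to 89.1 | 67% |

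Examples: 0.60 × 0.90 = 0.54 and 0.95 × 0.90 = 0.855. For the last share, 0.10 × 0.975 / 0.145 = 67%.

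For any exacerbation the true 60% falls outside the interval at w = 10% but not at 5%. For hospitalisation the true 95% falls outside at both.

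**The contradictory part alone.** Each 1% of participants who start another biologic lowers the reported value by p × 1 point: 0.60 points at p = 60% and 0.95 points at p = 95%. The rest of w is study withdrawal.

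**The case against.** The opposing case has several sound parts.

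- **Few people may be affected.** Other biologics are prohibited up to Week 64 (Protocol Table 6), and Protocol 7.2 expects withdrawal to be uncommon. This limits the size of the effect but does not settle which estimand is reported.
- **The no-imputation statement is not a firm conflict.** SAP 3.3 and Protocol 9.4.1 rule out imputation only beyond what is defined for each outcome, and the failure rule is such a definition.
- **Part of the remedy is already planned.** SAP 4.2.2.4 and 4.2.3.4 tabulate participants with zero events, and SAP 4.1.1.2 tabulates withdrawals. A reader could compare these with the 4.2.4 figures, though nothing prompts it. The zero-event percentage also treats short follow-up as complete, so it errs upward.
- **The current rule is conservative and visible.** It is written out in full. Starting another biologic may reflect poor control, in which case censoring there would be optimistic.
- **Kaplan-Meier as the main analysis would leave the protocol.** Protocol 9.4.3.2 specifies a number and proportion with 95% CI. This stands, and it bears on how the fix is made.

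A reader might infer that everyone who stops tezepelumab early is failed. SAP 3.3.1.1 shows otherwise. A reader might also see an inconsistency with SAP Table 4, where a biologic starter can succeed on the pre-biologic steroid dose. That is a different variable with its own stated rule, and it shows no error here.

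**Conclusion.** For participants who start another biologic, SAP 4.2.4.2 is wrong as written: a composite rule is applied where the SAP 4.2 table and Protocol 9.4.1 state a hypothetical one, and SAP Section 2 does not declare it. This affects all three proportions at both time points. For study withdrawals there is no contradiction with the table, only an unstated choice that does not fit the endpoint's label.

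Under the assumed w of 5% to 10%, the shift is 3 to 6 points for a true 60% and 4.75 to 9.5 points for a true 95%. These sizes rest on assumed rates and on leaving being unrelated to the event.

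The stronger reading, that withdrawals drive these proportions, is not supported. No rates are given, and for any exacerbation event-free leavers stay a clear minority of failures (4% to 17% above). It is plausible only for the hospitalisation versions, where they would be about half to two thirds of failures at w of 5% to 10%, and 28% at w of 2%.

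**What to change.** Reconcile the passages in one of two ways.

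1. Align SAP 4.2.4.2 with the stated strategy. Report the Kaplan-Meier probability of being free of a first event at Weeks 28 and 52 with 95% CI, censoring at the start of another biologic and at withdrawal or last exacerbation assessment.
2. Keep the current rule, declare a composite strategy for these proportions in the SAP 4.2 table and in Section 2, and state there how study withdrawal is handled.

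In both cases, rename the current proportion *completed the period without exacerbation and without another biologic*, report the number of participants in cell [b], and show the censored estimate beside it.

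The cost is SAP wording and one standard analysis. If the Kaplan-Meier estimate replaces the proportion as the main result, the departure from Protocol 9.4.3.2 also has to be declared. The censored estimate assumes non-informative censoring; the retained composite brackets it from below, since it treats every leaver as a failure.

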4.2.4.3 Handling of Dropouts and Missing Data

No data imputation.

4.2.4.4 Primary Analysis of Secondary Endpoint

The number and proportions of participants who did not experience an exacerbation, an exacerbation associated with hospitalisation or ER visit and an exacerbation associated with hospitalisation are summarised using the same approach described for the primary endpoint (Section 4.2.1.4) on the FAS.

4.2.4.5 Additional Analyses of Secondary Endpoint

No additional analysis.

4.2.4.6 Subgroup Analyses of Secondary Endpoint

The analysis described in Section 4.2.4.4 is repeated in subgroups described in Section 4.2.1.7.

4.2.4.7 Interim Analysis of Secondary Endpoint

No presentation for interim analysis.

4.2.5 Secondary Endpoint - Proportion of participants with ≥ 50% reduction from baseline in daily maintenance OCS dose at Week 28 and Week 52

4.2.5.1 Definition

The proportion of participants with $\geq 50\%$ reduction from baseline in daily maintenance OCS dose is calculated at Week 28 and at Week 52.

4.2.5.2 Derivations

The percent change from baseline in final daily maintenance OCS dose is defined as presented in Section 3.3. The baseline and final daily maintenance OCS dose derivation are defined in Sections 3.3.1.2 and 4.2.1.2. The proportion is calculated as the number of participants with the percent change from baseline $\geq 50\%$ divided by total number of participants in the FAS.

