3.3 General Considerations

In general, continuous endpoints are summarised using the mean, the standard deviation, median, minimum value, and maximum value, and the categorical endpoints are summarised using frequency counts and percentages, as well as a two-sided 95% CI for proportions computed using exact Clopper-Pearson method. Time to event data is presented graphically using Kaplan Meyer curve.

Absolute change from baseline is defined as (post-baseline value – baseline value). The percent change from baseline is defined as {(post-baseline value – baseline value)/baseline value)}*100. Baseline calculations are defined in the Section 3.3.1.2.

For participants' proportion calculation, the denominator is the number of participants in the Full Analysis Set defined in Section 4.1.2 unless otherwise stated.

No imputation performed beyond the approach defined for outcome measures. Imputation for partial date is detailed in the Appendix A.

Unless specified otherwise, the daily maintenance OCS dose, including the daily OCS at baseline (Section 3.3.1.2) and the final daily OCS dose (Section 4.2.1.2), is defined based on the prescribed maintenance dose of OCS, expressed as a dose per day, at the time of the relevant visit. If a participant is on a fixed daily dose, then the OCS dose is defined as that prescribed dose. If the participant is on every other day regimen (or different doses every other day), then the OCS dose is defined as the average amount prescribed to be taken each day. For example, should a participant be on a 10 mg every other day regimen of OCS, their OCS dose is defined as 5 mg.

Maintenance dose of OCS is collected on the ECSYSCRT eCRF page with a therapy reason of "Asthma maintenance dose", "Titration, due to asthma", "AI based on cortisol test", "Signs/symptoms of AI" and "Adrenal crisis". If the maintenance OCS doses with more than one therapy reasons (including only those mentioned earlier) are prescribed on the same day (e.g., "Asthma maintenance dose" and in addition "Signs/symptoms of AI"), then the sum of the doses are calculated.

Note that the prescribed OCS dose with therapy reason of "Asthma exacerbation per protocol" or "Worsening of asthma, without exacerbation" is not included in the daily OCS dose calculation. In case of overlapping OCS doses taken for asthma worsening or exacerbation with maintenance doses of OCS, the latter one is excluded from the daily OCS dose calculation.

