Endpoint	Popula tion	Intercurrent event strategy	Population level summary (analysis)	Details in section
Exploratory objective: To describe the ability of tezepe	elumab to	ezepelumab to improve Asthma Impairment and Risk Questionnaire (AIRQ)		
Change from baseline in AIRQ at Week 52	FAS	Same intercurrent event strategies as described for secondary objective related to exacerbation.	Unadjusted mean and SD	4.2.18
Proportions of AIRQ responders at Week 52			Proportion of participants with 95% CI	
Exploratory objective: To describe the ability of tezepelumab to improve Sino-nasal Outcome Test (SNOT-22)	elumab to	improve Sino-nasal Outcome Test (SNOT-22)		
Change from baseline in Sino-nasal Outcome Test (SNOT-22) at Week 28 and Week 52	FAS	Same intercurrent event strategies as described for secondary objective related to exacerbation.	Unadjusted mean and SD	4.2.19
Proportion of SNOT-22 responders at Week 28 and Week 52			Proportion of participants with 95% CI	
Exploratory objective: To describe participant satisfaction with change in daily OCS use	ion with	hange in daily OCS use		
Change from baseline in Participant Perception of OCS (PPOCS) score at Week 28 and Week 52	FAS	Same intercurrent event strategies as described for secondary objective related to exacerbation.	Proportion of participants with 95% CI	4.2.20
Exploratory objective: To evaluate the ability of tezepelumab to reduce exposure to SCS	elumab to	reduce exposure to SCS		
Mean daily exposure of systemic corticosteroids (mg/day) taken for asthma reasons over 28 and 52 weeks	FAS	Same intercurrent event strategies as described for secondary objective related to exacerbation.	Unadjusted mean and SD	4.2.21
Safety objective: To describe the safety and tolerability of tezepelumab	of tezepe	lumab		
Serious adverse events (SAEs), AE leading to discontinuation of IP (DAEs), and adverse events of special interest (AESI)	FAS	All data included in the analysis regardless of treatment discontinuation, change in background therapy ^b , or initiation of therapy with another biologic for treatment of asthma	Proportion of participants	4.6.2

^a Loss of asthma control is defined as asthma worsening or exacerbation. Asthma worsening is defined by an increase of ACQ-6 score ≥ 0.5 from baseline

^b Background therapies are collected within the CM eCRF form with Therapy reason "Disease under study".

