4.2.5.4 Primary Analysis of Secondary Endpoint

The number and proportion of participants with $\geq 50\%$ reduction from baseline in daily maintenance OCS dose are summarised using the same approach described for the primary endpoint (Section 4.2.1.4) on the FAS.

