4.2.6.2 Derivations

The percentage reduction from baseline in daily maintenance OCS dose at Week 28 and at Week 52 whilst maintaining asthma control is calculated as described in Section 3.3 and categorised as follows:

- Category 1: $\geq 90\%$ to $\leq 100\%$ reduction
- Category 2: $\geq 75\%$ to $\leq 90\%$ reduction
- Category 3: \geq 50% to <75% reduction
- Category 4: >0% to <50% reduction
- Category 5: no change or any increase.

The baseline and final daily maintenance OCS dose derivation are defined in Sections 3.3.1.1 and 4.2.1.2.

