4.2.19.2 Derivations

The SNOT-22 score is the sum of the 22 items and it ranges from 0 to 110. Higher scores indicate poorer outcomes. If one or more of the individual items is missing, the total SNOT-22 score is automatically set to missing (directly managed at the data entry level).

The absolute change from baseline in SNOT-22 score at a post-baseline visit is calculated as described in Section 3.3 on the FAS. Baseline value is derived as presented in Section 3.3.1.2.

Responder (Yes=1/No=0) is calculated on the FAS at each timepoint as follows:

- Responder: Absolute individual change from baseline in SNOT-22 score \leq -8.9
- Non-responder: Absolute individual change from baseline in SNOT-22 score > -8.9

The proportion of responders (non-responders) is calculated as the number of participants who reached the responder (non-responder) SNOT-22 threshold at each timepoint divided by total number of participants in the FAS.

Strategies of handling intercurrent events are presented in Section 4.2.

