4.2.19.4 Primary Analysis of Exploratory Endpoint

The absolute values and absolute changes from baseline in SNOT-22 score are summarised using descriptive statistics over time. The number and proportions of SNOT-22 responders, non-responders and missing data are also presented over time. All data available at primary DBL is presented, which includes data beyond Week 28 (see Section 3.1).

The analyses are performed based on the FAS.

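### Two SAP derivation rules are wrong as written: the ≥50% OCS reduction rule has the wrong sign, and the SNOT-22 responder rate divides by the whole FAS although only a sinusitis subset completes the questionnaire

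*SAP*

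**What the plan says.** **OCS reduction (secondary endpoint).** SAP 3.3: "The percent change from baseline is defined as" the post-baseline value minus the baseline value, divided by the baseline value, times 100. SAP 4.2.5.2 takes percent change from that section and continues: "The proportion is calculated as the number of participants with the percent change from baseline" at or above 50%, over the total FAS. The sections on either side describe a reduction. SAP 4.2.5.1 says the proportion with at least 50% "reduction from baseline in daily maintenance OCS dose is calculated at Week 28 and at Week 52", and SAP 4.2.5.4 says the number and proportion with at least 50% "reduction from baseline in daily maintenance OCS dose are summarised using the same approach described for the primary endpoint". SAP 4.2.6.2 sorts the same dose changes into five categories, the last being "Category 5: no change or any increase".

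**SNOT-22 (exploratory endpoint).** The endpoint table in SAP 4.2 lists "Proportion of SNOT-22 responders at Week 28 and Week 52", summarised as a proportion with a 95% CI. SAP 4.2.19.2 takes those who reached the responder (or non-responder) "SNOT-22 threshold at each timepoint divided by total number of participants in the FAS". SAP 4.2.19.4 adds: "The number and proportions of SNOT-22 responders, non-responders and missing data are also presented over time", on the FAS. Protocol 8.1.5.5 limits the questionnaire to participants who have symptoms of chronic sinusitis at screening. SAP 4.2.19.1 also limits it to a subset, but describes that subset by sinusitis history, timed at baseline.

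**The concern.** For the OCS endpoint, the one line that tells the programmer whom to count contradicts the endpoint it implements. The proportion in 4.2.5 should equal Categories 1 to 3 of 4.2.6.2 added together; the literal rule gives part of Category 5 instead. The line serves Week 28 and Week 52, and the subgroup tables through 4.2.5.6.

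For SNOT-22, the FAS has no sinusitis restriction, so people who were never given the questionnaire are in the denominator. The responder rate and its interval then do not describe response among those assessed. The missing-data row would also mix people who were never asked with people who were asked and did not answer, so real missingness could not be read from the table.

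**Working it through.** The documents give no figure for either rule. The plan's only related figure is the precision at 300 participants in SAP 1.3: ±5.8 points around 50%. Clopper-Pearson limits for 150/300 give ±5.80 points, so the interval method used below matches the plan's.

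**1. Sign of the OCS rule**

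Formula (SAP 3.3): (post − baseline)/baseline × 100. The lowest possible value is −100%, at a final dose of 0 mg.

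| Baseline to final dose | Percent change | ≥ 50% (as written) | ≤ −50% (as intended) |
|---|---|---|---|
| 10 to 0 mg | −100% | not counted | counted |
| 20 to 5 mg | −75% | not counted | counted |
| 10 to 5 mg | −50% | not counted | counted |
| 10 to 7.5 mg | −25% | not counted | not counted |
| 10 to 15 mg | +50% | counted | not counted |

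The same holds over a wider range. Take baseline doses of 5 to 40 mg (the range in protocol inclusion criterion 3) in 2.5 mg steps, which gives 15 values, and final doses of 0 to 40 mg in 0.5 mg steps, which gives 81 values. The step sizes are a choice made for illustration. Of the 15 × 81 = 1215 pairs, 349 are reductions of at least 50% and 322 satisfy the written rule. The overlap is 0, and all 322 fall in Category 5.

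Elsewhere the SAP signs its decrease-based thresholds correctly: ACQ-6 ≤ −0.5 (4.2.15.2), SGRQ ≤ −4 (4.2.17.2), AIRQ ≤ −2 (4.2.18.2) and SNOT-22 ≤ −8.9 (4.2.19.2). Section 4.2.5.2 is the exception.

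**2. SNOT-22 denominator**

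If a share *s* of the FAS is eligible, all of them answer, and a fraction *r* of them respond, the rate on the FAS is *s* × *r*, which cannot exceed *s*. Neither *s* nor *r* is in the documents. Assumptions: FAS = 300, *s* from 20% to 60%, *r* of 40% or 60%.

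| Eligible | *r* = 60%: subset rate (95% CI) | *r* = 60%: FAS rate (95% CI) | *r* = 40%: FAS rate | Never eligible |
|---|---|---|---|---|
| 60 (20%) | 36/60 = 60.0% (46.5–72.4) | 36/300 = 12.0% (8.5–16.2) | 24/300 = 8% | 240 |
| 120 (40%) | 72/120 = 60.0% (50.7–68.8) | 72/300 = 24.0% (19.3–29.2) | 48/300 = 16% | 180 |
| 180 (60%) | 108/180 = 60.0% (52.4–67.2) | 108/300 = 36.0% (30.6–41.7) | 72/300 = 24% | 120 |

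In no row does the FAS interval at *r* = 60% contain 60%. The last column is 300 minus the number eligible. With only responder, non-responder and missing rows on an FAS basis, those participants have no place but the missing row.

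SAP 4.2.14.2 handles the parallel case differently: ACTH results are divided by the number who needed that test, and repeat cortisol results by the number who needed the repeat.

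**The case against.** On the OCS rule, the endpoint is called a reduction in the section heading, 4.2.5.1, 4.2.5.4, SAP Table 1, the SAP endpoint table and the protocol, so one line out of step is unlikely to mislead a programmer. The SAP also uses 3.3 loosely elsewhere: 4.2.6.2 says its percentage reduction is calculated as in 3.3 and then applies positive cut-offs. That stands as evidence of intent, and output review would probably catch the clash. It does not make the line right. Section 4.2.6.2 at least names its quantity a reduction, whereas 4.2.5.2 names percent change and sets a positive threshold. It is also fair that the dose grid adds little to the algebra: a reduction can never equal +50%.

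On SNOT-22, the FAS is the SAP's declared default denominator and is used for the other questionnaire responder rates, and the rate among those assessed can be rebuilt from the printed counts as responders/(responders + non-responders). Both statements are true. But the other questionnaires are not restricted to a subset, 3.3 allows a different denominator where one is stated, and rebuilding the rate neither corrects the specified proportion and its interval nor separates never-asked from missing. That never-eligible participants fall in the missing row is an inference, because the SAP does not define the row. The eligible share and response rates above are assumptions.

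**Conclusion.** Both points hold. As written, 4.2.5.2 counts no participant with a reduction of at least 50%, and everyone it does count belongs in Category 5. This follows from the formula alone and needs no assumption. It is a specification error in a secondary endpoint whose intent is plain.

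The SNOT-22 rate in 4.2.19.2 is the true rate multiplied by the eligible share. How far it is diluted depends on a share the documents do not give; under the stated assumptions a true 60% prints as 12% to 36% and a true 40% as 8% to 24%. The SAP's description of the eligible group also differs from the protocol's. The protocol decides who completes the questionnaire, so the data collected do not change, but the SAP does not correctly name the group needed as denominator.

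The SAP should be corrected on both points. The primary endpoints and the sample size are unaffected.

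**What to change.** - **SAP 4.2.5.2:** count participants with percent change from baseline ≤ −50%. Percent reduction ≥ 50% is equivalent if percent reduction is defined as minus the percent change. Add a programming check that the count equals Categories 1 to 3 of 4.2.6.2. For that check, end Category 2 below 90%, as SAP Table 1 and protocol 9.4.3.2 do; the text of 4.2.6.2 as available here shows ≤ 90%, which would count a reduction of exactly 90% twice.
- **SAP 4.2.19.2 and 4.2.19.4:** use FAS participants with symptoms of chronic sinusitis at screening as the denominator for the responder, non-responder and missing rows, and state how many are eligible.
- **SAP 4.2.19.1:** align the description of the subset with protocol 8.1.5.5.

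The cost is two one-line edits and one wording alignment, with no new data. The SNOT-22 interval becomes wider: under the assumptions above, a 60% rate has a 95% CI of 46.5–72.4% with 60 eligible and 52.4–67.2% with 180.
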